#### 6.0 Study Procedures

#### Screening Visit

After informed consent has been obtained, the subject's medical history and medications will be discussed and documented. A physical exam, including measurement of height, weight, and vital signs, will be performed. Blood will be collected for a comprehensive metabolic panel, complete blood count (CBC), Hemoglobin A1c, thyroid stimulating hormone (TSH), and free T4. A urine or serum pregnancy test will be completed on female subjects of child-bearing potential. Whenever possible, we will combine these research screening tasks and procedures with standard of care tasks and procedures to decrease the burden placed on the patient. This information will be acceptable from standard of care visits as far back as 6 months prior to the day the patient is identified as a possible candidate. Even if the patient has had these assessments completed during a standard of care visit, it is up to the discretion of the Principal Investigator to use them or require an updated set of assessments. The Study Investigator may also request a second screening blood draw to confirm eligibility. Inclusion/exclusion criteria will be reviewed to confirm that the subject meets study eligibility requirements. Patients may be asked to stop spironolactone and eplerenone, if the participant is using them for cosmetic or excessive hair growth, 4-6 weeks prior to the study visit at Vanderbilt's CRC, as these medications may affect the results of aldosterone and renin.

#### Study Visit

Subjects will arrive at the Vanderbilt Clinical Research Center (CRC) after having fasted for at least 8 hours. We will collect a urine sample, including urine sodium and

creatinine. Women of childbearing potential will undergo a pregnancy test. Subjects will then lie supine (flat on their back). After approximately 30 minutes of lying supine, baseline resting energy expenditure will be assessed using indirect calorimetry (metabolic cart, described below). At the completion of the metabolic cart, and while subject is still lying supine, we will collect a blood sample, including basic metabolic panel, measurements of NPs and measurements of the RAAS system (renin and aldosterone), insulin, glucose, and markers of lipolysis (glycerol, free fatty acids). Subjects will then undergo a subcutaneous fat biopsy, as described below. Subsequently gene expression will be assessed for markers of "beiging" (including UCP1), as well as other cardiometabolic pathways including the natriuretic peptide pathways. Protein expression and histology may also be assessed if sufficient tissue is obtained. Subjects will also undergo a dual-energy x-ray absorptiometry (DXA) scan to assess body composition. In the event of scheduling issues, the DXA scan may be performed within about 2 weeks before or after the main study visit. Subjects will need to remain lying supine for the majority of the study visit (about 2 hours, before and during the metabolic cart, blood draw, and fat biopsy).

For women, these study visits will be scheduled to coincide with the follicular phase of the menstrual cycle to minimize the impact of hormonal changes on energy expenditure (EE) and on measurements of renin-angiotensin-aldosterone (RAAS) system.

#### Other study procedures

Phlebotomy: Blood draws will occur as outlined above.

Subcutaneous adipose tissue biopsy: Participants will undergo percutaneous subcutaneous adipose tissue biopsies on the abdomen (peri-umbilical region). This procedure will be performed by a trained study physician or nurse practitioner. With the subject laying in a supine position, an approximately 10 cm diameter area will be cleaned with a chlorhexidine swab lateral to the umbilicus. A fenestrated sterile drape will be placed to establish the sterile field. Approximately 20 ml of 1% lidocaine will be applied to anesthetize the skin. A small (approximately 0.5 cm) incision is made through the skin with a scalpel, within a few centimeters lateral to the umbilicus. Upon examination of the participant's body habitus, the trained proceduralist may choose to first infiltrate normal saline into the subcutaneous adipose tissue if the proceduralist feels that this may improve the success of obtaining sufficient adipose tissue. Then, a TULIP 2.7mm liposuction cannula with a syringe attached is inserted and moved parallel to the skin at a rate of approximately 1 Hz without breaking suction and with a twisting motion. The sampling continues until a goal of approximately 10 ml of tissue (approximately 9.5 g) is collected. The syringe is then removed, antibiotic ointment applied, a steri-strip is placed, and the incision is covered with an adhesive bandage. The tissue will be rinsed from blood. Then, tissue samples will either be placed immediately in liquid nitrogen and stored at -80 degrees Celsius until analysis, or processed immediately. The bandages will be removed after 24 hours, and steri-strips are left in place until they fall off.

Indirect Calorimetry (Metabolic Cart): Resting energy expenditure will be determined by indirect calorimetry, using a metabolic cart (a ventilated hood system).

Hemodynamic monitoring (blood pressure monitoring and heart rate monitoring by cardiac telemetry): We will monitor heart rhythm and rate during the study. This will be done by placing sticky pads (electrodes) on the chest. The sticky pads are connected to wires (leads) that hook up to a machine and display heart rhythm, rate and blood pressure.

Substrate oxidation (lipid oxidation and carbohydrate oxidation): Respiratory exchange ratio will be determined using VO2 and VCO2 measurements, which is determined via indirect calorimetry, and collected at the same time points as energy expenditure.

Biomarkers: Blood, urine, and tissue samples will be coded for subject confidentiality. These samples will be measured for a wide array of cardiometabolic parameters and inflammatory markers. Possible techniques include RNAseq and metabolomics techniques. Additional samples will be frozen and stored for possible future investigation.

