# Aim 1: Determine whether beige adipose tissue markers differ between obese and lean individuals.

We plan to enroll and conduct subcutaneous adipose biopsies on approximately 155 adult participants (aged 18-55 years; approximately 50 lean and 105 obese participants). We will quantify expression of genes indicative of "beiging" in subcutaneous adipose tissue biopsies and determine whether gene expression differs based on obesity status. In a secondary analysis, we will determine whether these beige adipose tissue markers differ by race.

Aim 2: Determine whether beige adipose tissue markers and energy expenditure are associated with natriuretic peptide receptor expression in adipose tissue and circulating natriuretic peptide levels. We will examine these associations in approximately 155 adult participants, as described in Aim 1.

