Due to recruitment setbacks related to COVID-19, some samples and data previously collected from another study, Cardiovascular Effects of GLP-1 Receptor Activation (P.I., Dr. [name] (Vanderbilt University Medical Center (VUMC) IRB# 170213, ClinicalTrials.gov Identifier: NCT03101930) will be included to help meet our enrollment goals for the obese subject population. In this prior study (VUMC IRB# 170213), obese individuals underwent the same study procedures that we are performing in the present study as outlined below (subcutaneous adipose tissue biopsy, indirect calorimetry, DXA body composition scan), and thus the samples/data have already been collected. These samples were of similar inclusion criteria as the currently recruiting study, with the minor adjustment of age criteria of up to 65 years of age. For the prior study (VUMC IRB#170213), subjects signed a consent form which indicated their consent for their samples/data to be used for future research. Samples provided from this study will be de-identified for our use. There are approximately 122 obese individuals from this prior study with available baseline samples/data relevant to any of our endpoints, of whom approximately 80 individuals have adipose biopsy data (our primary endpoint). The inclusion of these samples will enable us to analyze baseline data for approximately 105 obese subjects with adipose biopsy data (primary endpoint) (from the subjects that we are able to personally recruit, as well as the previously collected samples/data from the prior study).

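### About 80 of 105 obese biopsies come from an earlier obese-only study, and nothing requires them to be assayed together with the lean samples, so an assay-run shift could enter the lean-obese UCP1 contrast

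*Combined protocol and SAP*

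**What the plan says.** **Source of the samples.** Section 5.0 says that material from a completed study "will be included to help meet our enrollment goals for the obese subject population". It describes about 122 obese people from that study with some relevant baseline material, "of whom approximately 80 individuals have adipose biopsy data (our primary endpoint"). The stated result is the ability to "analyze baseline data for approximately 105 obese subjects with adipose biopsy data (primary endpoint"). Aim 1 gives the group sizes as "approximately 50 lean and 105 obese participants". By subtraction, about 25 obese participants are newly recruited. No lean participant comes from the earlier study.

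**Comparability.** Section 5.0 states that in the earlier study "obese individuals underwent the same study procedures that we are performing in the present study as outlined below", and names the biopsy, calorimetry and DXA. It adds "thus the samples/data have already been collected". It does not say whether UCP1 had already been measured on that tissue.

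**Handling and assay.** The biopsy paragraph in section 6.0 says that "tissue samples will either be placed immediately in liquid nitrogen and stored at -80 degrees Celsius until analysis, or processed immediately". It gives no rule for which route supplies the UCP1 assay. The Biomarkers paragraph leaves the laboratory technique open. Samples are coded, but for confidentiality. No section sets extraction or assay runs, mixing of groups within a run, or laboratory blinding to group.

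**Model.** Section 10.0 regresses UCP1 expression, normalised to a housekeeping gene, on BMI. Age and sex are the only covariates named.

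**The concern.** Normalised expression is a relative measure. A difference between extraction or assay runs can move every sample in a run by a similar amount. If the borrowed obese samples were run separately, or enter as results already obtained, that movement falls on about three quarters of the obese group and on none of the lean group. The planned regression has no term to absorb it, so the estimate would be the biological difference plus most of the run difference. Either sign is possible: a shift could create a lean-obese difference or hide one.

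The timing also matters. Run allocation can be chosen freely before the assays. Afterwards it can be repaired only by re-assaying whatever tissue remains, or by giving up much of the precision that the borrowed samples were meant to add. Aim 2 measures that use borrowed samples or results, such as natriuretic peptide receptor expression, face the same question, although no size is worked out for them here.

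**Working it through.** **Inputs from the documents:** 50 lean and 105 obese (Aim 1); 80 borrowed obese (section 5.0), so 105 − 80 = 25 new obese; target difference 0.7 units or 0.45 SD, type 1 error 0.05 (section 10.0). The implied SD is 0.7/0.45 = 1.56 units. **Assumed:** the size of any shift, and a two-sided test, because section 10.0 does not state sidedness.

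**1. The plan's own figure.** Section 10.0 claims 80% power for 0.45 SD with 100 subjects. With 50 per group, power = Φ(0.45/√(1/50 + 1/50) − 1.96) = Φ(2.25 − 1.96) = 61% two-sided (73% one-sided). The stated 80% is not reproduced. That is a separate matter; here 0.45 SD serves only as a yardstick.

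**2. Bias.** If a shift s affects the 80 borrowed samples and no others, the obese mean moves by s × 80/105 = 0.762s and the lean mean does not move.

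**3. False positives with no true difference.** SE = √(1/50 + 1/105) = 0.172 SD. The rejection rate is Φ(bias/SE − 1.96) + Φ(−bias/SE − 1.96). The simulated column is the rejection rate in 20,000 two-sample t-tests.

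| Assumed shift (SD) | Bias (SD) | Bias (units) | Bias as share of 0.45 SD | False positives, formula | Simulated |
|---|---|---|---|---|---|
| 0.1 | 0.08 | 0.12 | 17% | 7% | 8% |
| 0.2 | 0.15 | 0.24 | 34% | 14% | 15% |
| 0.3 | 0.23 | 0.36 | 51% | 26% | 26% |
| 0.5 | 0.38 | 0.59 | 85% | 60% | 58% |

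A shift of 0.45 × 105/80 = 0.59 SD would by itself produce the whole target difference.

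**4. Separation by a source or batch term.** The lean-obese contrast then rests on 50 lean v 25 new obese. SE = √(1/50 + 1/25) = 0.245. The difference detectable with 80% power is (1.96 + 0.84) × 0.245 = 0.69 SD. Power at 0.45 SD is Φ(0.45/0.245 − 1.96) = 45%. The pooled 50 v 105 comparison without such a term has 75% power and a detectable difference of 0.48 SD.

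**5. Mixed runs.** When the same shift falls on half of each group, simulated bias is essentially zero. False-positive rates are 4.8%, 4.2% and 2.9% for shifts of 0.25, 0.5 and 1.0 SD. The fall below 5% is run variation left in the residual, which is a reason to include batch in the model.

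**6. Handling route alone.** Bias = (difference between groups in use of a route) × (route effect). If use differs by 25 percentage points and the effect is 0.5 SD, the bias is 0.125 SD. If use is equal, it is zero.

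These figures are for an unadjusted two-group contrast. If BMI is analysed as a continuous variable, the borrowed samples still all lie in the obese range, so the same confounding applies. Its size cannot be computed without the BMI distribution.

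**The case against.** The strongest reply is that the documents show no batch effect and no separate assay run. The shift is assumed, and the scenario is an extreme one: every borrowed sample is shifted and no other sample is. Housekeeping-gene normalisation may remove part of a shift, such as one due to RNA input, though not a difference in platform or probe. Section 5.0 says that the earlier study used the same procedures and names the biopsy. Because the handling sentence sits inside the biopsy description, common handling is a fair reading. Section 5.0 also speaks of de-identified samples being provided, which fits physical tissue that can still be assayed. Run layout and blinding often sit in a laboratory manual, which is not among the documents.

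Most of this stands, and it limits the point to a risk that the plan leaves open. It does not close that risk. The assurance in section 5.0 does not reach RNA extraction or assay runs, and its wording admits existing data as well as samples.

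A reader might infer from the two handling routes that the comparison is already biased. The documents do not support this. The wording applies to all participants, no section ties a route to a group, and immediate processing may refer to the protein or histology work mentioned under Study Visit.

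**Conclusion.** The point holds as a cheap improvement to the pooled analysis. Followed as written, the plan permits an assay-run difference to enter the primary contrast at about 76% of its size. Over assumed shifts of 0.1 to 0.5 SD, that is a bias of 0.08 to 0.38 SD and about 7% to 60% false positives. The range depends on the shift being confined to the borrowed samples and on no credit for normalisation.

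Two stronger readings are tempting. The first is that no analysis could separate laboratory from biology. That would be true only if lean and obese samples never shared a run. Here about 25 obese participants are recruited in the same study as all the lean ones, so a source or batch term, or an analysis of new participants only, can identify the contrast. The price is precision: about 45% power at 0.45 SD. The second is that mixing samples within runs would remove the whole problem. It deals with extraction and assay runs only. The borrowed tissue has already been collected, and its past handling and storage time remain tied to the obese group.

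**What to change.** **Sections 5.0 and 6.0:**
- State how the borrowed tissue was handled, how much remains, and whether UCP1 has already been measured on it.
- Where tissue remains, extract and assay it with the new tissue, in runs that each contain lean, new obese and borrowed obese samples. Keep the laboratory blind to group.
- For the UCP1 endpoint, use for new tissue the route that the borrowed tissue had. Fixing a route before that is known could itself create a difference between groups. Record route and storage time for every sample.

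**Section 10.0:**
- Include assay batch in the model.
- Do not pool UCP1 results from an earlier run into the primary contrast unless re-assayed samples bridge the two runs.
- Add a sensitivity analysis in newly recruited participants (about 50 lean v 25 obese), to be read with its low power in mind, because mixed runs cannot correct past handling or storage.

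**Cost:** protocol wording, reagents for the borrowed tissue, and waiting until runs can be mixed. No participant has an extra procedure. The real downside is the loss of borrowed subjects whose earlier results cannot be bridged. If that were all of them, the obese group would fall from about 105 to about 25.

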#### **Table Of Events:**

Procedure	Screening Visit	Main Study Visit
Informed Consent	X	
Medical History & Physical exam	X	
Vital Signs, height, weight	X	X
Pregnancy test	X	X
Clinical Laboratory sample collection	Х	X
Fat Biopsy		X
Metabolic Cart		X
DXA scan		X

# 7.0 Risks

Fasting: Inconvenience and hypovolemia. To minimize risks of hypovolemia, subjects will be instructed to drink plenty of fluids the day before the visits, and we will measure subjects' blood pressure and heart rate upon arrival for their study visits and during the study visits. Also, there is a potential risk of hypoglycemia while fasting. However, the risk of hypoglycemia in healthy individuals while fasting for this amount of time is low.

Subjects will be monitored for signs and symptoms of hypoglycemia throughout the study visits.

Phlebotomy: The risks associated with phlebotomy in healthy individuals are minimal. Risks include pain, bruising, inflammation, and rarely fainting and infection. Other possible risks include low fluid status in the body and anemia (low blood counts). Risks will be minimized by excluding subjects with anemia or history of hypotension. Subjects will be advised to drink plenty of the fluids the night before the study visit, and after the study visit.

Hemodynamic monitoring (blood pressure monitoring and heart monitoring by cardiac telemetry): A non-invasive technique with no symptoms aside from possible minimal discomfort.

Percutaneous subcutaneous adipose tissue biopsy: The biopsy procedure will be performed by a study physician or nurse practitioner trained in this technique. The percutaneous subcutaneous adipose tissue biopsy procedure is associated with low risk. Possible risks of the biopsy procedure include pain, local skin irritation, bleeding, bruising, and hematoma at the site. There is potential risk for local or systemic infection, more severe bleeding, or a small scar; however, the risk of these events is extremely low.

Lidocaine: May cause local discomfort during injection, or a rash, redness or soreness at the injection site. In rare cases, lidocaine could potentially cause hypersensitivity reactions, confusion, or induce a transient alteration in heart rhythm; to reduce this risk, suction will be applied to the syringe prior to injection to ensure the lidocaine is not being injected into a vessel.

Metabolic cart: This is a non-invasive technique which involves placing a ventilated hood over the subject's head for approximately 30 minutes. The technique carries no risks other than possible minimal discomfort. Subjects with history of claustrophobia will be excluded from the study.

Dual Energy X-ray Absorptiometry (DXA): Radiation risk is very minimal. DXA uses very low dose radiation, and the expected total exposure for each participant is in the range of 7 millirem, which is equivalent to approximately 9 days of background radiation.

Subjects will be offered lunch after completing study procedures that must be performed in a fasted state (metabolic cart, blood draw, and abdominal fat biopsy).

# 8.0 Reporting of Adverse Events or Unanticipated Problems involving Risk to Participants or Others

Participants should and will be instructed to notify study personnel regarding any adverse events or unanticipated problems. Adverse events will be reported to the IRB per IRB policy. Also, all serious and unanticipated adverse events or problems involving risks to subjects that may possibly be or are known to be related to the research activity will be reported promptly to the IRB office per IRB policy.

A Data Safety Monitor will monitor the study. The Data Safety Monitor will provide ongoing evaluation of studies' progress including patient accrual and retention and monitoring of adverse events. Reports will be submitted to the Data Safety Monitor for review approximately every 12 months.

## 9.0 Study Withdrawal/Discontinuation

Subjects may withdraw from the study at any time and should notify study personnel in writing if they wish to withdraw from the study. Subjects may request their biological samples to be destroyed at any time. However, any data or biological samples that have already been used for research cannot be destroyed.

Subjects may be discontinued from the study at the discretion of the investigators' (possible reasons listed below).

Possible reasons for withdrawal/discontinuation from study include, but are not limited to:

- Noncompliance with procedures
- Decision by participant/participant withdraws consent
- Loss to follow-up
- Change in patient's health status that makes them no longer eligible for study.
- Development of a significant medical condition specified in the exclusion criteria
- In female subjects, becoming pregnant during study
- Significant adverse event deemed by investigator to preclude continued participation

#### 10.0 Statistical Considerations

Sample size justification: A total of 100 subjects will provide 80% power to detect a minimum difference between lean and obese groups of 0.7 units of UCP1 mRNA expression normalized for housekeeping gene mRNA gene expression (primary analysis). This represents a metabolically meaningful difference of approximately 0.45 standard deviations between lean and obese groups. These calculations are based on a Type 1 error rate of 0.05, and interindividual variations in UCP1 gene expression reported in prior studies. Since there is only 1 main study visit, dropouts should not be an issue in this study. However, there is a low likelihood that some adipose tissue samples may be inadequate quantity or quality. Even if some adipose tissue samples are of insufficient quantity or quality, a sample size of 80 would still provide 80% power to detect a minimum difference between groups of 0.75 units in UCP1 normalized mRNA expression, which represents a metabolically meaningful difference of approximately 0.48 standard deviations between lean and obese groups.

Of note, the above sample size calculation was based on the original enrollment goal of 100 subjects. Now that we have the benefit of including some samples from a previously completed study, our statistical power to answer our scientific questions will be improved.

Statistical Analysis: The primary analysis will determine whether adipose tissue gene expression of UCP1 differs between lean and obese individuals. To assess this, we will use multivariable linear regression, with UCP1 gene expression as the outcome variable, and BMI as the independent variable. The multivariable linear regression will be adjusted for covariates that may impact markers of beige adipose tissue, including age and sex. The null hypothesis is that UCP1 gene expression will not differ based on BMI. Secondary analyses include whether UCP1 gene expression differs by race and whether expression of additional "beiging" markers differ by obesity status. Like the primary analysis, the secondary analyses are analyzing a continuous outcome variable. Thus, the statistical approach for the secondary analyses will be similar to that described for the primary analysis.

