#### 2.0 Rationale and Specific Aims

NP levels differ by obesity status and race in epidemiologic studies, and NPs appear to promote "beiging" of adipose tissue in animals. However, whether gene expression of beige adipose tissue differs by obesity status and race has not been established in humans. Human mechanistic studies investigating the relationships of beige adipose tissue markers with obesity status, race, and the natriuretic peptide system are limited. We propose an innovative physiologic study in which we will quantify adipose tissue gene expression and energy expenditure in states of relative NP deficiency in humans, namely in obese and black individuals. Our overarching postulate is that obese and black individuals have NP deficiencies that contribute to less beige adipose tissue and lower energy expenditure. Thus, we propose the following aims:

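### The 80% power stated for 100 and for 80 subjects is not reproduced: a two-sided comparison of two equal groups gives about 61% and 56%

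*Combined protocol and SAP*

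**What the plan says.** The sample size justification in Section 10.0 makes two power statements for the primary analysis of UCP1 expression.

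- With 100 subjects: "A total of 100 subjects will provide 80% power to detect a minimum difference between lean and obese groups of 0.7 units". The text equates this to "approximately 0.45 standard deviations between lean and obese groups".
- With 80 subjects, should some tissue samples prove unusable: "a sample size of 80 would still provide 80% power to detect a minimum difference between groups of 0.75 units". The text equates this to about 0.48 SD.

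On inputs it says "These calculations are based on a Type 1 error rate of 0.05" and cites between-person variation from prior studies. It does not give the SD, the sidedness of the test, the split between lean and obese, or any R-squared for covariates.

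The planned model is a linear regression "with UCP1 gene expression as the outcome variable, and BMI as the independent variable", adjusted for covariates including age and sex. The section discloses that "the above sample size calculation was based on the original enrollment goal of 100 subjects" and adds that samples from a completed study will improve power. Aim 1 puts the current target at "approximately 50 lean and 105 obese participants". No power figure is given for that sample.

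**The concern.** A standardised difference of 0.45 with 100 subjects in two groups falls well short of 80% power at a conventional two-sided 0.05, and 0.48 with 80 subjects falls further short. The two SD figures also do not move with sample size as they should.

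These are the only power figures in the plan for its primary analysis. Both differences are described there as metabolically meaningful. If power is really about 61% and 56%, the chance of missing such a difference at those sample sizes is about 39% and 44%, not 20%. The study now plans about 155 subjects, so those miss rates do not describe the final analysis. But a reader who takes 80% as the starting point and is told that power has improved will expect clearly more than 80%. That matters most if the UCP1 comparison comes out null.

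**Working it through.** **Inputs from Section 10.0 and Aim 1.** N = 100 with d = 0.45 SD (0.7 units); N = 80 with d = 0.48 SD (0.75 units); alpha 0.05; current target 50 lean and 105 obese.

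**Assumed, because not stated.** Two-sided test, equal groups at N = 100 and N = 80, no gain from covariates.

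**Implied SD.** 0.7/0.45 = 1.556 and 0.75/0.48 = 1.563 units. The two agree, so unit conversion does not explain the gap. Rounding in the second pair allows 0.745/0.485 = 1.54 to 0.755/0.475 = 1.59.

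**Method.** Noncentrality δ = d / √(1/n₁ + 1/n₂), with n₁ + n₂ − 2 degrees of freedom; power is the probability that the noncentral t exceeds the critical value.

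- 50/50: δ = 0.45/0.200 = 2.25, critical value 1.984, power **60.6%**.
- 40/40: δ = 0.48/0.2236 = 2.147, critical value 1.991, power **56.4%**.
- 50/105: δ = 0.45/0.1718 = 2.619, critical value 1.976, power **74.0%** (79.3% at 0.48 SD).

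The stated 80% is therefore not reproduced for 100 or for 80 subjects.

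**Difference detectable with 80% power (two-sided, unadjusted)**

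| Groups | SD | Units at SD about 1.56 | Units at SD 1.54–1.59 |
|---|---|---|---|
| 50/50 | 0.566 | 0.88 | 0.87–0.90 |
| 40/40 | 0.634 | 0.99 | 0.97–1.01 |
| 50/105 | 0.484 | 0.75 | 0.74–0.77 |

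**Other readings, one at a time**

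| Reading | N = 100, 0.45 SD | N = 80, 0.48 SD |
|---|---|---|
| One-sided 0.05, equal groups | 72.2% | 68.6% |
| Favourable rounding (0.455, 0.485 SD) | 61.5% | 57.2% |
| N taken as per group (normal approximation) | 89% | 86% |
| R-squared needed for 80%, two-sided | 0.37 | 0.43 |
| Continuous BMI, 12 assumed scenarios | 65–82% | 61–78% |

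- *Unequal groups* lower power. At N = 100, 40/60 gives 58.8%, 35/65 gives 56.6% and 30/70 gives 53.3%.
- *R-squared* is 1 − (d/detectable d)²: 1 − (0.45/0.566)² = 0.37 and 1 − (0.48/0.634)² = 0.43. For 50/105 at 0.45 SD it is 1 − (0.45/0.484)² = 0.14.
- *Continuous BMI* assumes a linear effect with the same lean–obese gap, lean mean 22.5 and SD 1.8, obese mean 34, 36 or 38 and SD 3, 4, 5 or 6. BMI is taken as uncorrelated with age and sex. The documents give no BMI distribution. Power reaches 80% in 1 of 12 scenarios at N = 100 and in none at N = 80. With one-sided testing as well, the ranges are 76–89% and 72–86%.

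**Scaling check.** Going from 100 to 80 subjects, the detectable SD difference should grow by √(100/80) = 1.118. The stated figures grow by 0.48/0.45 = 1.067, at most 0.485/0.445 = 1.090 after rounding. So, small degrees-of-freedom effects aside, no single sidedness, split and R-squared makes both SD figures 80%-power values. The raw units can be reconciled: 0.67 rounds to 0.7, and 0.67 × 1.118 = 0.75.

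**The case against.** The strongest reply is that the two-group t test is not the planned model. Section 10.0 regresses UCP1 on BMI. If BMI enters as a continuous variable with a linear effect, the spread of BMI within groups adds power. The eligibility criteria set no upper BMI limit, so a wide obese distribution is possible. With an obese mean of 36 and SD of 8, two-sided power is about 84–85% at N = 100 and 80–82% at N = 80. With mean 34 and SD 7 it is about 85–86% and 81–83%. A modest R-squared combined with continuous BMI would help further. The study's postulate is also directional ("obese and black individuals have NP deficiencies that contribute to less beige adipose tissue and lower energy expenditure"), which could have led to a one-sided calculation. Finally, the plan says openly that its figures belong to a superseded target.

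Part of this stands. The 80% cannot be called impossible under every unstated input, and the 61% and 56% rest on labelled assumptions. But the text expresses the effect as a difference between lean and obese groups, and its null hypothesis is stated as no difference by BMI, without direction. The spreads that rescue both figures are hard to credit above a floor of 30. A mean of 34 with SD 7 means an average excess of 4 over the floor with an SD of 7, and a mean of 36 with SD 8 an average excess of 6 with an SD of 8. Both are strongly right-skewed. The plan states none of these inputs, so they show under-specification and do not support the 80%.

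The disclosure about the target of 100 also stands, and the claim of improved power is right in direction. It does not correct the baseline or supply the current figure.

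**Conclusion.** The concern holds. For a two-sided 0.05 comparison of two equal groups without covariate gain, 100 subjects have 61% power at 0.45 SD and 80 subjects have 56% at 0.48 SD. One-sided testing, unequal groups and rounding, taken singly, do not reach 80%. Covariates or continuous BMI could, but only with R-squared values or BMI spreads that the plan does not give.

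The practical effect is limited by the larger sample. At 50 versus 105, power at 0.45 SD is 74% two-sided and unadjusted, 83% one-sided, 80% with an R-squared of about 0.14, and about 80–95% with continuous BMI under the 12 assumed scenarios. The plan should be corrected on this point, but the enlarged study is not shown to be underpowered. Figures in units depend on the back-calculated SD of about 1.56.

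**What to change.** In Section 10.0, state the SD and its source, the sidedness, the allocation, whether BMI is continuous or lean/obese, and any assumed R-squared. Then restate the figures on that basis.

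For a two-sided 0.05 comparison of two equal groups with no covariate gain and an SD of about 1.56 units, the text would say that 100 subjects give 80% power for about 0.57 SD (0.88 units) and 80 subjects for about 0.63 SD (0.99 units).

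Keep the sentence on improved power and follow it with a figure for the current target: 50 lean and 105 obese give 80% power for about 0.48 SD (0.75 units), and 74% power at 0.45 SD, two-sided and unadjusted.

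If the calculation used one-sided alpha, an R-squared or continuous BMI, say so and recompute all three figures under that choice.

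The cost is wording in one section, and less favourable figures for 100 and 80 subjects. No extra enrolment is needed.
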